Given the potential for Maraviroc to augment rehabilitation training, we will carry out a trial of Maraviroc in patients with disabilities severe enough to have required inpatient stroke rehabilitation and, based on our preclinical data, who can start the drug intervention within 6 weeks of stroke onset. We plan a parallel group, randomized controlled pilot trial at three sites, UCLA SOM, Yale University SOM in New Haven, and Burke Neurological Research Institute in White Plains, NY, to gather enough entries in a shorter time and to better generalize the results of this phase II/III pilot trial. We will compare usual post-stroke care plus placebo versus Maraviroc given for 8 weeks in 60 participants (up to 66 to account for dropouts). The primary outcome measurements will be gains in walking and functional use of the affected upper extremity, continuously monitored remotely, as well as formally assessed at 4 and 8 weeks after initiating the drug and at 6 months (primary endpoint) post stroke onset. To try to maximize the amount of practice that is most relevant to the primary outcome measurements and determine whether or not Maraviroc can enhance the effects of training, as hypothesized, all participants will be monitored by mobile health devices we developed and will receive weekly encouragement, based on device data, to walk, reduce sedentary time, and reach and grasp in the home in between usual care therapies. The amount of use of these telerehabilitation devices will be a nested substudy of feasibility.

We will look for a behavioral marker of the potential effect of Maraviroc by testing each subject while on and off the assigned medication with several commonly used neuropsychological tests of motor and hippocampal learning.

The trial will be registered at ClinicalTrials.gov with ethical approval from the UCLA medical IRB.

Hypothesis 1: Subjects who take Maraviroc plus outpatient and home-based rehabilitation therapy managed remotely will improve significantly more in the primary outcomes of walking speed and upper extremity function by the Action Research Arm Test (ARAT) compared to the placebo drug group at the 6-month post stroke assessment.

Hypothesis 2: The feasibility of home-based telerehabilitation practice will be revealed by the finding that at least 75% of all participants will have achieved compliance for at least 150 minutes of walking and 100 minutes of reach and grasp practice weekly.

Methods

Consent Process:

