A data manager at UCLA will review all incoming data from the 3 sites for completeness and quality, as well as ensure proper use of the systems (e.g. make sure devices are charged regularly, automatic data uploads occur without problems, and practice data are processed correctly). The study staff at each site will assist the UCLA staff to help solve technical problems with the equipment and interact with subjects around difficulties in patient participation. At the weekly call by UCLA staff, participants will be queried from a script about any possible medical complications. Such potential adverse events will be immediately reported to [name] who will contact his participants or contact the local PI at Burke or Yale to interview their subjects and then report back to [name].

Outcome Measurements:

The primary outcomes will be a timed walking speed over 10 meters by the blinded physical therapist and the ARAT for UE function performed by the blinded therapist. These will be obtained at baseline, then after 4 weeks on assigned medication, within 5 days of the last medication dose (8 weeks) and again at 6 months post stroke onset.

Secondary outcomes obtained at the end of drug treatment and at 6 months after stroke onset by the blinded observer will include the Fugl-Meyer Motor Assessment score for both lower and upper extremities, clinic-based 3-min walking distance, and the Stroke Impact Scale score related to quality of life. We will also assess for satisfaction and self-efficacy for practice and exercise (see Table). Exploratory studies will examine dose of practice based on LEAP data (duration, number of repetitions of reach and grasp of objects) and for walking (total daily walking practice time, sedentary time, and walking bouts of more than 5 minutes), and self-ratings about self-efficacy for exercise.

Statistical Analyses:

A recent observational trial (Lohse and Lang, 2016) found that walking speed increases at 0.1m/s per month and the ARAT increases by 2.9 points monthly within the time frame as this trial.

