For the walking speed outcome, the evaluable sample size of 30 in each group will have 80% power to detect a difference in means of -0.206 (m/s), the difference between an assumed usual care walking speed of 0.51 (SD=0.28) and an assumed intervention group mean walking speed of 0.716. This assumes that the common standard deviation in the two groups and a two group t-test with a 0.05 two-sided significance level. The estimates for the mean and standard deviation for walking speed come from the LEAPS RCT (Duncan, N Engl J Med, 2011). We plan to enroll 66 patients to account for an expected 10% drop-out rate. The t-test used for the power calculation is a simplification of the mixed effects analysis plan for the primary endpoints.

For the ARAT sum score, analysis is based on a statistical power of 80% with an alpha of 5% for detecting a meaningful difference of 6 points, i.e., a 10% change, which has been suggested by several completed trials. In a stroke trial, the standard deviation was 8 points measured at 2 weeks post stroke. Again, a sample size of 60 plus 10% dropout rate should suffice.

Primary Analyses: As appropriate, t-tests, Wilcoxon rank sum, or chi-square tests will be employed to evaluate differences in baseline clinical characteristics between trial participants. Using the mixed effects model for *Hypothesis 1* should provide greater power than the t-test as it will account for the repeated observations of the endpoints over time. For *Hypothesis 2*, we will look at one aspect of the feasibility of home-based practice as the ratio of those who achieve at least 150 minutes of weekly walking (composed of bouts that exceed 5 minutes) and 100 minutes of weekly upper extremity practice using the LEAP with the whole group as the denominator. We anticipate that >75% will achieve this by the end of the intervention, based upon our preliminary studies using these devices in a chronic hemiparetic stroke population.

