Secondary Analyses: Secondary outcomes listed in the Table will be evaluated using t-tests, Wilcoxon rank sum tests, or chi-square tests as appropriate. One planned secondary analysis will compare outcomes based on whether or not participants can extend their wrist and at least 3 fingers at least 5 degrees at time of randomization, to assess for possible differences in drug responses between those with higher compared to lower levels of initial motor control. Another will compare outcomes in those who achieve the practice goals of Hypothesis 2 to those who do not in relation to drug assignment. We will not likely have enough subjects to do more than look for interesting potential future hypotheses.

Safety Committee:

A Safety Committee will serve both research sites. It will include the study statistician, a physician and an allied health clinician with training in stroke rehabilitation. It will meet before the start of the trial, every 6 months, after the first 10 subjects have completed the 2-month drug intervention, and as needed (e.g., serious adverse reaction).

Confidentiality:

All data will be entered from the study sites at UCLA, Yale and Burke into the RedCap database that will be monitored at UCLA by the study statistician for completeness. All materials related to the trial for UCLA entries will be stored in a locked cabinet in a locked room by the coordinator.

References

Dobkin BH. A Rehabilitation-Internet-of-Things in the Home to Augment Motor Skills and Exercise Training. *Neurorehabil Neural Repair*. 2016 Nov 23. pii: 1545968316680490.

Table. Measurement tools and testing schedule

Category	Test	Schedule		During treatment: at end of 4 and 8 weeks	6 mo outcomes
		Entry	Weekly f/u for 2 mo		
Study Procedures					
Screening	X	X			
Inclusion/Exclusion	X	X			
Informed Consent	X	X			
AE Assessment	X		X		
Demographics	NIH standard	X			
Disability	FIM	X			X
Mobility	10-m walk speed	X		X	X
Upper extremity fx	ARAT	X		X	X
Overall Impairment	NIHSS	X			X
Motor Impairment	Fugl-Meyer motor score	X		End of tx	X

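### The 80% ARAT power rests on an SD measured at 2 weeks post stroke, so it is unsupported at the 6-month primary endpoint and should be stated conditionally, with the contrast adjusted for entry ARAT

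*Combined protocol and SAP*

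**What the plan says.** The Aims and Outcome Measurements sections make 10-m walking speed and the ARAT the two primary outcomes. Both are measured at baseline, after 4 weeks on drug, at the end of drug (8 weeks) and finally "at 6 months (primary endpoint) post stroke onset".

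For the ARAT, Statistical Analyses states that the "analysis is based on a statistical power of 80% with an alpha of 5% for detecting a meaningful difference of 6 points". The only variability input is this: "In a stroke trial, the standard deviation was 8 points measured at 2 weeks post stroke". The paragraph concludes that 60 patients plus a 10% dropout allowance will be enough. No source is named for the SD. The preceding paragraph, on walking speed, takes its mean and SD from a named published randomised trial.

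The Interventions section puts drug start most often at 4-6 weeks after onset. Statistical Analyses describes the t-test behind the power calculation as a simplification of a planned mixed effects model. Primary Analyses expects that model to have more power because it uses the repeated measurements. No figure is attached to that expectation, and entry ARAT is not named as a covariate.

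**The concern.** A power statement is only as good as the SD at the time and in the form in which the outcome will be compared. Here the SD comes from a time point that this trial does not analyse: it precedes the usual baseline and is about 5.5 months before the endpoint. Nothing in the documents links it to the spread of ARAT at 6 months or to the residual spread after the planned modelling.

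At stake is how the ARAT result will be read. A null result would be set against a stated 80% chance of detecting 6 points. If the effective SD were materially above 8, that chance would be lower, and the null would be weaker evidence of no effect than the plan implies.

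**Working it through.** **Inputs from Statistical Analyses and Randomization.** Difference 6 points; SD 8; alpha 5%; 1:1 allocation; 30 evaluable per group. The figure of 30 per group is given under walking speed ("the evaluable sample size of 30 in each group will have 80% power"), and its total of 60 is repeated for the ARAT. Sidedness is also given only for walking speed ("a two group t-test with a 0.05 two-sided significance level") and is assumed to carry over to the ARAT.

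**Step 1: reproduce the plan's figure.** For a two-group t-test with n per group, the noncentrality is δ / (SD × √(2/n)), with 2n − 2 degrees of freedom.

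- 6 / (8 × √(2/30)) = 6 / 2.066 = 2.90; critical t on 58 df = 2.00; power = 81.5%.
- The smallest n per group giving 80% is 29 (58 in total).

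The claim of 80% with 60 evaluable patients therefore reproduces. A one-sided 5% test would give about 89%, so the two-sided reading is the one that fits.

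**Step 2: the largest SD that keeps 80%.** Solving power = 80% at n = 30 and δ = 6 gives SD ≈ 8.16. That is 8.16 / 8 = 1.02, or 2% above the assumed value.

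**Step 3: range under assumed SDs.** The documents give no 6-month SD, so these values are assumptions. Power is for an unadjusted comparison at 30 per group.

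| Assumed SD | Power | n per group for 80% |
|---|---|---|
| 8 | 81.5% | 29 |
| 9 | 72% | 37 |
| 10 | 63% | 45 |
| 12 | 48% | 64 |
| 15 | 33% | 100 |

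**Step 4: what baseline adjustment could recover.** With correlation r between entry and 6-month ARAT (assumed, since the plan gives none), residual SD = SD × √(1 − r²).

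- SD 12, r = 0.7: 12 × √0.51 = 8.57; power 76%.
- SD 12, r = 0.8: 12 × √0.36 = 7.20; power 89%.
- The r needed for 80% is √(1 − (8.16/SD)²): about 0.58 at SD 10, 0.73 at SD 12 and 0.84 at SD 15.

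**Step 5: why the form of adjustment matters.** A change-from-baseline contrast has SD × √(2(1 − r)), assuming equal SDs at both times. At SD 12 and r = 0.7 this is 12 × √0.6 = 9.30, with power 69%. The three options at these assumed values are therefore 48% (unadjusted), 69% (change score) and 76% (entry ARAT as covariate).

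**The case against.** The strongest reply is that no shortfall has been shown. Every power figure below 80% uses an assumed SD, and the unadjusted figures describe a t-test that is not the planned primary analysis. The mixed effects model uses repeated measurements, and the hypotheses are framed as gains. At SD 12 and r = 0.8, adjusted power would exceed the plan's figure. Any trial sized to 80% also has little slack, and this one is called a pilot.

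Most of that stands. What it does not supply is a basis for the 80%. The gain from the mixed model is asserted without a correlation, and a repeated-measures model does not by itself say whether entry ARAT is a covariate. The pilot label does not excuse the figure, because Hypothesis 1 is a formal between-group comparison and the plan states a power for it.

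Two stronger arguments are tempting, and the documents support neither.

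- **Recovery.** A reader might note that "the ARAT increases by 2.9 points monthly within the time frame as this trial" and infer that some 16 points of recovery (5.5 months × 2.9) must widen the spread. A rise in the mean says nothing about the SD. On a bounded score the spread may widen or narrow, and the rate is quoted only for this trial's time frame, not from week 2.
- **Mixed severity.** Secondary Analyses compares "those with higher compared to lower levels of initial motor control", and a reader might infer that mixing the two groups pushes the SD above 8. The source trial is unnamed, so its SD may already include mixed severity. The documents give no gap between the groups. A difference present at randomization is also one that baseline adjustment can remove.

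**Conclusion.** The concern holds in a limited form. The ARAT calculation is arithmetically correct for an SD of 8. Its 80% is unsupported at the 6-month endpoint because the SD comes from an unnamed trial at 2 weeks and no endpoint SD, correlation or range is given. The condition for 80% is an effective SD of at most about 8.16, given 30 evaluable per arm, a two-sided 5% test and a 6-point difference.

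It would be wrong to infer that the trial is underpowered for the ARAT. The documents do not show that the 6-month SD exceeds 8, and the planned model may offset a larger one. The span from 33% to 89% in the working shows how much depends on two unstated quantities; it is not an estimate of the trial's power.

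**What to change.** 1. In Primary Analyses, specify that the 6-month ARAT treatment contrast in the mixed effects model is adjusted for entry ARAT, which the measurement schedule already collects.
2. In the ARAT sample-size paragraph, replace the closing assurance that the sample is adequate with a conditional statement: 60 evaluable patients give 80% power for 6 points (two-sided 5%) only if the baseline-adjusted residual SD is at most about 8.16.
3. Add a short table labelled as assumed values. Unadjusted power: SD 9 72%, SD 10 63%, SD 12 48%, SD 15 33%. Baseline-adjusted power at SD 12: r 0.7 76%, r 0.8 89%. If the sponsor has a sourced 6-month SD or correlation from a comparable inpatient-rehabilitation population, give it and mark the matching entry.

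**Cost.** No extra patients, visits or measurements. The stated ARAT power becomes conditional and less favourable. Item 1 is a small change to the analysis specification, not wording alone.

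### The plan does not say how the Entry score enters the treatment comparisons; adjusting for it would probably gain precision at almost no cost

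*Combined protocol and SAP*

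**What the plan says.** Aims sets the target time with "and at 6 months (primary endpoint) post stroke onset", and Hypothesis 1 predicts that the Maraviroc group "will improve significantly more in the primary outcomes of walking speed and upper extremity function" than placebo. Of walking speed and ARAT, Outcome Measurements says: "These will be obtained at baseline, then after 4 weeks on assigned medication", followed by the 8-week and 6-month visits. Entry values of both primary outcomes will therefore exist.

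Under Statistical Analyses, the sample-size text states: "The t-test used for the power calculation is a simplification of the mixed effects analysis plan for the primary endpoints". Primary Analyses adds that this model "should provide greater power than the t-test as it will account for the repeated observations of the endpoints over time". It lists no fixed effects, covariates, covariance structure or contrast, and does not say whether the Entry value is a covariate, one of the responses, or unused.

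Two uses of baseline data are explicit. Tests "will be employed to evaluate differences in baseline clinical characteristics between trial participants", and Secondary Analyses plans a comparison by "whether or not participants can extend their wrist and at least 3 fingers at least 5 degrees at time of randomization". Neither adjusts the treatment comparison.

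For the rest: "Secondary outcomes listed in the Table will be evaluated using t-tests, Wilcoxon rank sum tests, or chi-square tests as appropriate". The Table schedules Entry values for Fugl-Meyer, Stroke Impact Scale and CES-D, among others.

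**The concern.** Hypothesis 1 speaks of improving more, with 6 months as the endpoint. That wording fits at least three analyses: a raw comparison at 6 months, a comparison of change from Entry, and a comparison at 6 months adjusted for Entry. All are valid in a randomised trial, but they do not have the same power. Repeated visits do not by themselves deliver the extra power that the plan expects at 6 months; that depends on how baseline is used.

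With 30 evaluable participants per arm, the choice affects what the trial can detect. If it is left open until the data are unblinded, the analyst can also choose among results.

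**Working it through.** **Inputs from Statistical Analyses.** Walking speed: n = 30 per arm, SD 0.28, difference 0.206 m/s, two-sided alpha 0.05. ARAT: difference 6 points, SD 8.

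**Assumed input.** r, the correlation between the Entry and 6-month values. The documents do not give it, so a range is shown.

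**Step 1: the plan's figure.** SE = 0.28 × √(2/30) = 0.0723. Non-centrality = 0.206 / 0.0723 = 2.849. The non-central t with 58 df gives 80.0%, which agrees with the plan.

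**Step 2: three analyses of the 6-month value.**
- Raw t-test: SE = SD × √(2/30), 58 df.
- Change score: SE = SD × √(2(1−r)) × √(2/30), 58 df.
- Baseline-adjusted (ANCOVA): SE = SD × √(1−r²) × √(2/30) × √(57/56), 57 df. The factor 57/56 on the variance allows for expected chance imbalance at baseline.

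Example at r = 0.5: adjusted SE = 0.0723 × √0.75 × √(57/56) = 0.0632, non-centrality 0.206 / 0.0632 = 3.26, power 89.4%. For the change score, √(2 × 0.5) = 1, so its SE equals the t-test's and power is 80.0%.

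| r | Raw t-test | Change score | Adjusted |
|---|---|---|---|
| 0 | 80.0% | 50.9% | 79.3% |
| 0.1 | 80.0% | 55.1% | 79.7% |
| 0.2 | 80.0% | 60.1% | 80.9% |
| 0.3 | 80.0% | 65.8% | 82.9% |
| 0.5 | 80.0% | 80.0% | 89.4% |
| 0.7 | 80.0% | 95.1% | 97.3% |

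Difference detectable with 80% power at r = 0.3, 0.5, 0.7: adjusted 0.198, 0.180, 0.148 m/s; change score 0.244, 0.206, 0.160 m/s; raw 0.206 m/s throughout. Equating detectable differences, adjustment overtakes the raw t-test at r = 0.135 and loses to the change score only above r = 0.964.

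In 40,000 simulated trials per value of r, ANCOVA power at r = 0, 0.2, 0.3, 0.5, 0.7 was 79.1%, 80.5%, 82.9%, 89.1%, 97.3%. Its type I error at r = 0.5 was 4.92%.

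**Step 3: does a mixed model capture the gain anyway?** SE of the 6-month contrast by generalised least squares, complete data, compound symmetry, r = 0.3, 0.5, 0.7:
- Post-baseline visits only, with a separate arm difference at each visit: 0.0723 at every r, the same as the t-test.
- All four visits with a free arm difference at Entry, contrast 6 months minus Entry: 0.0855, 0.0723, 0.0560.
- All four visits with arm means constrained equal at Entry: 0.0690, 0.0626, 0.0516.

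Only the last, or conditioning on Entry, gains at all three values of r. A single common effect over the three post-baseline visits, if truly constant at 0.206 m/s, would have 97.0%, 92.9% and 88.0% power. Repeated visits can therefore help, but that is not the 6-month contrast.

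**Step 4: ARAT.** Raw t-test 81.5%; adjusted 84.3%, 90.5%, 97.7% at r = 0.3, 0.5, 0.7. These are indicative only, because the SD was measured at 2 weeks post stroke and ARAT is a bounded sum score.

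**The case against.** The strongest reply is that the primary model is unwritten, not shown to be unadjusted. Baseline is the first measurement listed for the primary outcomes, so it may well be among the repeated observations. If the team intends equal arm means at Entry, the gain is already there. This stands, and it is why the point is that the role of baseline is not stated. It does not close the gap, since including Entry as a response with a free arm difference gains nothing for the raw 6-month difference and loses power for the change contrast when r is below 0.5.

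The gain also rests on an r that nobody has shown. Eligibility limits the range of baseline function, which could lower r, and correlation may decay over time. If adjacent visits correlate at 0.5 and the decay is first-order, r = 0.125, which is below break-even, and adjusted power is 79.9%. With adjacent correlation 0.7, r = 0.343 and power is 84.0%. So a gain is likely but not guaranteed, and its size is unknown.

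The secondary outcomes have no stated SD or effect, so no gain can be calculated for them; the argument there is general. Finally, this is a pilot, the unadjusted test is valid, and the model proposed below is one acceptable specification among several. All of that is fair and limits the point to a recommended improvement.

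**Conclusion.** The point holds as a precision improvement, not an error. The 80% power and the 60 evaluable participants are right for the unadjusted t-test. What is missing is any statement of how Entry values enter the Hypothesis 1 model or the secondary comparisons. For walking speed at 6 months, the open readings run from 65.8% to 82.9% power at r = 0.3, and from 80.0% to 89.4% at r = 0.5. The direction in favour of adjustment holds for r between about 0.13 and 0.96; the size depends on the assumed r. The calculations assume complete data, equal SDs at Entry and 6 months, and a linear relation between the two.

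**What to change.** Before unblinding, write out the Hypothesis 1 model. For walking speed and for ARAT, model the 4-week, 8-week and 6-month values with categorical visit, treatment-by-visit and baseline value-by-visit terms and an unstructured within-subject covariance. Alternatively, include baseline as a response with arm means constrained equal. Name the 6-month treatment difference as the primary contrast.

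For continuous secondary outcomes with an Entry value of the same measure, such as Fugl-Meyer, Stroke Impact Scale and CES-D, replace the t-test with ANCOVA on that value. Keep rank-based or chi-square tests where ANCOVA does not suit, such as single Likert ratings.

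The cost is wording only, since the Entry values are already scheduled. Adjustment uses one degree of freedom at the 6-month contrast, worth about 0.02 percentage points of power. Nearly all of the worst-case loss, from 80.0% to 79.3% at r = 0, comes from chance baseline imbalance.

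Site terms are a separate decision. Adding two non-prognostic ones would give 77.8%, 79.4%, 81.5%, 88.2% and 96.8% at r = 0, 0.2, 0.3, 0.5 and 0.7, so they are not free and are not part of this recommendation.

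### The wrist-and-finger-extension analysis aims at differences in drug response, but the comparison it describes contains no treatment contrast; the difference in drug effect between subgroups should be named as the estimate

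*Combined protocol and SAP*

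**What the plan says.** All of the relevant text is under Statistical Analyses in the combined protocol and SAP.

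- **The comparison.** Secondary Analyses states: "One planned secondary analysis will compare outcomes based on whether or not participants can extend their wrist", together with at least three fingers, by at least 5 degrees, at randomization.
- **Its purpose.** The same sentence gives the aim: "to assess for possible differences in drug responses between those with higher compared to lower levels of initial motor control".
- **The neighbouring analysis.** The next sentence does mention the arms: "Another will compare outcomes in those who achieve the practice goals of Hypothesis 2 to those who do not in relation to drug assignment".
- **Tests named.** The paragraph opens by saying that the secondary outcomes in the Table "will be evaluated using t-tests, Wilcoxon rank sum tests, or chi-square tests as appropriate".
- **The caveat.** The paragraph closes: "We will not likely have enough subjects to do more than look for interesting potential future hypotheses".
- **The primary model.** Primary Analyses plans a mixed effects model for Hypothesis 1. It states no term for baseline motor control and no interaction.

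No other section supplies a drug-by-subgroup contrast.

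**The concern.** A difference in drug response between two kinds of patient is effect modification: the drug-minus-placebo difference in one subgroup minus the same difference in the other. A comparison of outcomes between patients with and without extension is a different quantity. Patients with more initial motor control can be expected to finish with better arm function whatever they were given, so such a comparison mainly reflects prognosis.

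The wording leaves two easy routes, and neither estimates the target. One is to compare the subgroups with the arms pooled. The other is to test the drug separately in each subgroup and note which test is significant. At stake is the value of the analysis for its own declared use, which is to suggest hypotheses. A prognostic difference, or a chance difference between two p-values, could be read as a difference in drug response.

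**Working it through.** **Inputs from Statistical Analyses.** 30 evaluable patients per arm; two-sided alpha 0.05. Walking speed: difference 0.206 m/s, SD 0.28. ARAT: difference 6 points, SD 8.

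**Assumptions (not in the documents).** The subgroup split, taken from 50:50 to 80:20 with arms balanced within subgroup; the prognostic gaps in step 2; and the same SD in every cell.

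**1. The plan's own figure.** The two-sample t-test (noncentral t) with 30 per arm gives 80.0% power for 0.206 m/s, which matches the stated 80%. The ARAT figures give 81.5%.

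**2. The comparison taken literally, arms pooled.** Let *g* be the prognostic gap between subgroups on placebo, and *e*H and *e*L the drug effects with higher and lower motor control. With half of each subgroup on drug, the expected difference between subgroups is

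(*g* + *e*H/2) − *e*L/2 = *g* + (*e*H − *e*L)/2.

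The target is *e*H − *e*L. The comparison returns the prognostic gap plus half the target and cannot separate them. A simulation on the ARAT scale (20,000 runs, 15 patients per cell, SD 8) gave these proportions significant:

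| Scenario | Pooled comparison | Interaction test |
|---|---|---|
| No drug effect, *g* = 8 (1 SD) | 96.6% | 5.0% |
| Drug effect 6 in both subgroups, *g* = 8 | 95.8% | 5.1% |
| Drug effect 6 vs 0, *g* = −3 | 4.4% | 29.6% |

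In the third row the expected difference is −3 + 6/2 = 0, so real effect modification disappears.

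**3. Separate tests within subgroups.** Suppose the drug effect is identical in both subgroups at the planned size. With powers *p*1 and *p*2, P(exactly one significant) = *p*1(1 − *p*2) + *p*2(1 − *p*1).

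- Even split, 15 per arm in each subgroup. Walking speed: power 0.494, so 2 × 0.494 × 0.506 = 0.50. ARAT: power 0.509, so 2 × 0.509 × 0.491 = 0.50.
- 80:20 split, 24 and 6 per arm. Walking speed: 0.704 × 0.789 + 0.211 × 0.296 = 0.62. ARAT: 0.720 × 0.782 + 0.218 × 0.280 = 0.62.

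**4. Precision of the right estimate.** The standard error of the difference in drug effects is SD × √(2/*n*H + 2/*n*L), where *n*H and *n*L are patients per arm in each subgroup.

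- 50:50: √(2/15 + 2/15) = 0.516, so the SE is 0.28 × 0.516 = 0.145 m/s and 8 × 0.516 = 4.13 points.
- 80:20: √(2/24 + 2/6) = 0.645, so the SE is 0.181 m/s and 5.16 points.

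With the noncentral t on 60 − 4 = 56 degrees of freedom:

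| | 50:50 | 80:20 |
|---|---|---|
| Difference detectable with 80% power, walking speed | 0.41 m/s | 0.52 m/s |
| Difference detectable with 80% power, ARAT | 11.8 points | 14.7 points |
| Power if the difference equals the planned effect, walking speed | 28.8% | 20.2% |
| Power if the difference equals the planned effect, ARAT | 29.8% | 20.8% |

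Even at the even split, the detectable difference is twice the planned main effect (0.41/0.206 = 2.0; 11.8/6 = 2.0). These figures use the plan's t-test simplification; the repeated-measures model may do somewhat better.

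**The case against.** The strongest reply is that the purpose clause already speaks of drug response, which has no meaning without comparing arms. The authors may well intend to compare drug effects across the two strata and have simply worded it loosely. That stands. A reader might infer that the analysis will ignore treatment, or that it cannot show effect modification. The documents support neither; they show a comparison clause that does not state the contrast its purpose requires. The gap is still more than a missing detail, because following the words literally gives a different quantity, and the neighbouring analysis does mention drug assignment.

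A reader might also take the list of t-tests, Wilcoxon and chi-square tests as the method for this analysis. That sentence covers secondary outcomes in the Table. The extension analysis refers only to outcomes, which may include walking speed and ARAT, for which a mixed model is planned. Likewise, the plan does not describe testing within subgroups, so the 50% figure illustrates one unsuitable way to fill the gap and is not a property of the stated plan.

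Finally, the plan limits itself to looking for future hypotheses. This answers any suggestion that the result will fix eligibility for a later trial; nothing in the documents says so. It does not answer the point about the contrast, since the caveat concerns sample size, and more patients would not turn a prognostic comparison into one of drug effects.

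**Conclusion.** The point holds as a mismatch between a stated purpose and an incompletely stated comparison. The aim is effect modification, and no section gives the drug-by-subgroup contrast that would estimate it. The literal comparison mixes prognosis with half the quantity of interest. Contrasting separate p-values would suggest a spurious subgroup difference in about 50% of trials at an even split, and about 62% at 80:20, when the drug effect is the same in both.

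These sizes rest on the plan's effect sizes and SDs and on assumed splits; the simulation also rests on assumed prognostic gaps. The algebra in step 2 needs only balanced arms within subgroups. The consequence is confined to an exploratory analysis. The primary comparison, its sample size and its conclusion are untouched.

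**What to change.** State that this exploratory analysis estimates the difference in the 6-month drug effect between participants with and without wrist and finger extension at randomization. Obtain it from a drug-by-extension interaction in the planned mixed model, set up so that the 6-month contrast can be read off, or equivalently as the difference between the two subgroup-specific drug effects. Report it with its 95% confidence interval for ARAT and walking speed, and state that within-subgroup p-values will not be interpreted.

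The cost is a sentence or two of analysis text and a few model terms, with no new data, visits or patients. The downside is small: cells will hold about 15 patients at best, and fewer with an uneven split, so the interval will be wide. If the model with visit terms proves unstable, the simple difference of subgroup-specific effects serves. The change corrects what is estimated but does not make the analysis well powered, so the plan's hypothesis-generating label should stay.
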